Data from age- and gender-matched healthy comparison (HC) subjects that have participated in [¹⁸F]FPEB PET as part of other Yale approved protocols (HIC#1101007933, HIC#1111009365, HIC#2000027842/2000020186) will be recruited to participate in the fMRI portion of this study. These protocols currently obtain written consent from subjects to allow sharing of their information to other Yale research groups for recruitment purposes, along with use of their PET data for research purposes among collaborating groups. Thus, HC participants will not need to undergo an additional [¹⁸F]FPEB PET scanning, but may be asked to complete additional screening (e.g., structured interviews), and will be asked to complete appropriate assessments and an fMRI session. Additional community-recruited HC individuals may be enrolled (i.e., those that have not completed [¹⁸F]FPEB PET scanning) to participate in longitudinal MRI procedures consistent with Aim 5. These participants will undergo appropriate screening procedures to determine eligibility, may complete self-assessments and complete MRI scanning up to 30 days apart.

b. Subject screening, admission, and assessment

CUD subjects:

Recruitment of CUD subjects will include experienced, currently-using, non-treatment-seeking, medically-healthy, adult volunteers meeting criteria for cocaine-use disorder. CUD subjects that have agreed to participate in similar research at the Cocaine Research Clinic as part of another Yale approved protocol (e.g., HIC#2000029552) may be invited to participate. When possible, these individuals will be recruited to participate in the PET and fMRI portions of this study concurrently with their participation in the other protocols. Simultaneous participation in multiple studies will be permitted at the discretion of the Investigators only if it would lessen subject burden (i.e., minimizing inpatient residencies and repeated assessments) without impacting the integrity of either study. Additional CUD subjects may be recruited through community advertising (e.g., flyers), screened, consented, evaluated, admitted to the CNRU.

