CUD subjects. CUD subjects will be 20 experienced, currently-using, non-treatment-seeking, medically-healthy, adult volunteers meeting criteria for cocaine-use disorder (see inclusion/exclusion criteria below; Section I, item 8).

HC subjects. HC subjects will be 20 medically-healthy, adult volunteers that have participated in an [¹⁸F]FPEB scan as part of another Yale approved protocol (HIC#1101007933, HIC#1111009365, HIC#2000027842/2000020186), or that are recruited from the community (Aim 5). Subjects will be contacted to participate in the fMRI portion of this study, and may be asked to completed additional assessments and screening procedures (see inclusion/exclusion criteria below; Section I, item 8).

7. Subject Classification:

 Children	 Healthy	 Fetal material, placenta, or dead fetus
 Non-English speaking	 Prisoners	 Economically disadvantaged persons
 Decisionally impaired	 Employees	 Pregnant women and/or fetuses
 Yale students	 Females of childbearing potential	

NOTE: Is this research proposal designed to enroll children who are wards of the state as potential subjects?

YES NO

Since cocaine dependence often involves serious financial difficulties, it is also possible that some of our subjects may be economically disadvantaged persons. We will carefully screen all participants to make sure that the potential for improvement in their cocaine addiction is the primary motivation for participation. We may enroll females of childbearing potential. All females will be carefully assessed to ensure the absence of pregnancy both before and during study participation.

8. Inclusion/Exclusion Criteria:Inclusion criteria:*HC and CUD subjects:*

- Age 21 - 60 years
- Provide voluntary, written, informed consent
- Physically healthy by medical history, physical, neurological, ECG, and laboratory examinations

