Standard neuroimaging analysis. Analysis of PET and fMRI data will be performed using standard general linear modeling approaches using regions-of-interest (ROIs) and whole-brain analyses of variance (ANOVAs) in SPM12. ROIs will be defined using the Neuromorphometrics atlas (neuromorphometrics.com) and include basal ganglia structures, subdivisions of the cingulate and other prefrontal and parietal regions that exhibit high [¹⁸F]FPEB uptake (64) and are implicated in response inhibition (65). Standard analyses will be performed as the primary investigation of mGluR5 availability in CUD relative to HC, and will support findings from network-based analyses of fMRI and multi-modal fusion techniques.

Network-based analysis. Independent component analyses (ICA) of PET and fMRI data will be performed using the Group ICA of fMRI Toolbox (GIFT; icatb.sourceforge.net). This software package was designed by [name] (co-investigator) and colleagues for functional network analysis of fMRI data, and includes a source-based morphometry (SBM) toolkit for analysis of structural/static biomedical images (66). The principles of ICA for fMRI and PET are largely consistent and have been previously performed in parallel (67, 68)

Multi-modal data fusion. Joint-ICA (jICA), parallel-ICA (pICA) and linked-ICA (lICA) are implementations of the ICA principles to fully integrate, or 'fuse', multiple datasets into a single coherent analysis (69-71). jICA identifies a single set of independent sources (e.g., the same functional brain networks) present in datasets collected in the same individuals under multiple conditions. Thus, jICA is suited to examine activity of functional networks active during *both* resting-state and HABIT performance, and examine changes in network dynamics (i.e., 'connectivity'-like patterns of network-to-network interactions) between conditions, providing advanced insight into the organization of functional systems. By comparison, pICA combines multi-modal data collected in the same individuals, identifying a shared higher-order data structure present in datasets, but that originate from *separate* sources in respective modalities (e.g., receptor-availability networks and functional brain networks. Similar to pICA, lICA combines multiple outcomes from within modality groups (e.g. fMRI group: resting-state and HABIT activity, PET group: V_T and k₁ parameters) toward a more fully integrated fusion analysis.

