Relationships with self-administration and impulsivity. Standard analysis of variance (ANOVA) and linear regression models will be used to examine potential associations between the neuroimaging measures with subjective effects and behavior during cocaine self-administration (e.g., 'high', infusion intervals, doses) collected under and earlier versions of this protocol, and scores on self-report assessments of impulsivity and compulsivity. Additional analysis will explore relationships between neuroimaging measures and self-administration behavior with additional psychological and cognitive factors (e.g., depression, anxiety, neurocognitive performance), which may indicate use of these measures as covariates for primary analyses.

Power considerations. The proposed project will include 20 CUD and 20 HC participants. Prior research of mGluR5 differences in CUD (27), and our work of functional-network differences in addiction-vulnerable populations using the Go/NoGo task (39) indicate this sample will be sufficiently powered ($d's > .95$) for analysis at a threshold of $\alpha = .05$ (PET: non-centrality parameter (δ) = 3.60, critical $t_{38} = 1.81$, power ($1 - \beta$) = 0.96; fMRI: $\delta = 3.06$, critical $t_{38} = 1.54$, power ($1 - \beta$) = 0.93). The modified HABIT task is expected to be similarly powered to the Go/NoGo.

Pilot addendum. Standard within-subjects repeated-measures analysis will be conducted to investigate changes in mGluR5 availability and functional network parameters between time points. Mixed effects models will be performed to examine differences in functional brain activity (i.e., fMRI data) and task-performance in CUD relative to HC. While this has not been directly explored previously, prior research examining differences between-subjects suggests a robust change in mGluR5 during the first few weeks of cocaine abstinence [28]. For the current purposes, if hypothesized changes are observed, results will serve as pilot data to estimate effect sizes toward obtaining additional funding.

SECTION II: RESEARCH INVOLVING DRUGS, BIOLOGICS, RADIOTRACERS, PLACEBOS AND DEVICES

A. RADIOTRACERS N/A

1. *Name of the radiotracer:* [¹⁸F]FPEB
2. Is the radiotracer FDA approved? YES NO

If NO, an FDA issued IND is required for the investigational use unless RDRC assumes oversight

3. *Check one:* IND#59,121 or RDRC oversight (RDRC approval will be required prior to use)

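### Controls are matched on age and gender, but the CUD-HC models do not prespecify either as a covariate; adding both is a nearly free, modest gain in precision

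*Combined protocol and SAP*

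**What the plan says.** Section I, item 4.a (General design and overview) describes the comparison group as "Data from age- and gender-matched healthy comparison (HC) subjects". It gives no pairing rule, caliper or ratio. Item 8 sets eligibility for both groups at "Age 21 - 60 years".

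In Section I, item 13, the paragraph on standard neuroimaging analysis states: "Analysis of PET and fMRI data will be performed using standard general linear modeling approaches". It adds ROI and whole-brain ANOVAs in SPM12 and gives them their role: "Standard analyses will be performed as the primary investigation of mGluR5 availability in CUD relative to HC". No model terms are listed.

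The only mention of covariates comes later in item 13, in the paragraph on self-administration and impulsivity. Exploratory work on psychological and cognitive factors is planned, "which may indicate use of these measures as covariates for primary analyses". The examples are depression, anxiety and neurocognitive performance; age and gender are not among them.

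The power paragraph says "The proposed project will include 20 CUD and 20 HC participants" and uses a t statistic on 38 degrees of freedom. That is 20 + 20 − 2, an unpaired comparison with no covariates.

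**The concern.** Matching makes the groups alike on age and gender, so those factors contribute less to the variance of the group difference. An unadjusted two-group model does not see this. Its residual still contains the age and gender variance, so its standard error is larger than the real sampling variability of the difference. The study goes to the trouble of matching, and the analysis as written does not collect the benefit. With 20 per group that costs some precision on the PET and fMRI contrasts.

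If matching is loose, the problem differs: a remaining age or gender difference shifts an unadjusted contrast by the factor's slope times the difference in group means, and nothing in the written model removes it.

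There is also a prespecification gap. The plan already allows covariates to enter the primary analyses after exploration, so whether age and gender enter is left open.

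**Working it through.** **Inputs from the documents (item 13, power paragraph).** n = 20 per group; alpha 0.05, sidedness not stated; noncentrality δ = 3.60 (PET) and 3.06 (fMRI); df 38; stated power 0.96 and 0.93. Since δ = d·√(n/2) = d·√10, the implied effects are d = 3.60/3.162 = 1.138 (PET) and 3.06/3.162 = 0.968 (fMRI).

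**Assumed.** R², the within-group outcome variance explained by age and gender together, is not in the documents. The values 0, 0.1, 0.2 and 0.3 are used.

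**1. The plan's own figures.** Noncentral t on 38 df at the printed critical values (1.81 and 1.54) gives 0.961 and 0.934, so the stated powers reproduce. Those critical values have one-sided tail areas of 0.039 and 0.066, not 0.05, which is a separate matter for the power text. At two-sided 0.05 (critical t 2.024) unadjusted power is 0.939 (PET) and 0.847 (fMRI). Two-sided 0.05 is used below.

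**2. Standard error under exact matching.** With within-group SD 1, the unadjusted model works with √(2/20) = 0.316. The actual SD of the estimated difference is √(2(1 − R²)/20):
- R² = 0.1: √0.09 = 0.300
- R² = 0.2: √0.08 = 0.283
- R² = 0.3: √0.07 = 0.265

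Simulated matched pairs gave 0.297, 0.286 and 0.265, while the unadjusted model reported about 0.314 throughout.

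**3. Confidence interval width.** The ratio of adjusted to unadjusted is √(1 − R²) × t(36)/t(38) = √(1 − R²) × 2.028/2.024, which is 0.95, 0.90 and 0.84. The interval narrows by about 5%, 10% and 16%.

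**4. Test size and power.** These come from simulating 20 pairs with identical age and gender within each pair, each factor carrying half of R². The unadjusted model has 38 df and the adjusted model 36.

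| R² | Size, unadjusted | Size, adjusted | fMRI power (d = 0.97), unadjusted → adjusted | PET power (d = 1.14), unadjusted → adjusted |
|---|---|---|---|---|
| 0.1 | about 4% | about 5% | 0.86 → 0.88 | 0.95 → 0.96 |
| 0.2 | about 3% | about 5% | 0.87 → 0.91 | 0.96 → 0.98 |
| 0.3 | about 2% | about 5% | 0.88 → 0.94 | 0.97 → 0.99 |

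Repeat runs differ by up to about 0.01. As a cross-check, noncentral t on 36 df with δ/√(1 − R²) gives adjusted power of 0.881, 0.914 and 0.945 (fMRI) and 0.958, 0.975 and 0.987 (PET).

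**5. If R² = 0.** The formula gives 0.846 adjusted against 0.847 unadjusted for fMRI, and 0.939 for PET either way. That is the close-matching case, where only the 2 df are lost. If matching is loose, the covariates also correlate by chance with group, and the cost can reach about 2 to 3 power points.

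**The case against.** The strongest reply is that silence is not exclusion. Item 13 lists no model terms at all, a general linear model in SPM12 takes covariates readily, and the plan says covariates may enter primary analyses. This stands: a reader might infer that the plan has decided to leave age and gender out, and the documents do not show that. Nor do the 38 df settle it. They belong to a planning calculation, and leaving covariates out of one is a common and conservative simplification. What remains is that the adjustment is not prespecified.

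Four other readings go further than the documents allow.

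- **Larger power gains.** Comparing adjusted power with the formula value of 0.847 suggests fMRI gains of about 3, 7 and 10 points (0.881, 0.914 and 0.945 less 0.847). That baseline ignores matching, which raises the unadjusted test's true power as well. Compared like with like, the gain is about 2, 4 and 6 points.
- **False positives.** Under close matching the unadjusted test rejects too seldom, not too often. Bias would need a real imbalance, and the documents show none.
- **Both harms at once.** Conservatism needs close matching and uncorrected imbalance needs loose matching. With no matching method described, neither can be asserted; the point is that adjustment handles either.
- **Community controls distorting the PET contrast.** Item 4.a defines the added community HC as people without an FPEB scan, enrolled for Aim 5 longitudinal MRI. They cannot enter the PET comparison. Items 1 and 6 leave room for them in the fMRI sample only.

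Finally, R² is wholly assumed. That limits the size of the claim, not its direction.

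**Conclusion.** The point holds as a missing prespecification with a concrete better model, not as an error that threatens validity. Severity is modest. The loss is smallest for PET, about 1 to 2 points at the plan's own effect size, and about 2 to 6 points for fMRI. Unadjusted test size is roughly 4% to 2% where 5% is intended. These figures assume exact matching, R² between 0.1 and 0.3, effects as implied by the stated noncentrality values, and two-sided testing. If age and gender do not predict the outcome, there is nothing to gain and, under close matching, almost nothing to lose. Confidence is high that the covariates are unspecified and low on the exact magnitude.

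**What to change.** Add one sentence to Section I, item 13: age (continuous) and gender are covariates in every CUD-HC model (ROI, voxelwise and network-based), this adjusted analysis is primary, and the unadjusted result is reported as a check.

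No new data, visits or subjects are needed, since both variables must be known in order to match. The price is 2 of 38 degrees of freedom, with a worst case of about 2 to 3 power points if neither factor predicts the outcome and matching is loose. It is in effect a free improvement.

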HRP-503B – BIOMEDICAL RESEARCH PROTOCOL
(2016-1)

Protocol Title: Investigation of cocaine addiction using mGluR5 PET and fMRI

Principal Investigator: [name].

Version Date: MAR 28 2022

Clinicaltrials.gov Registration #: NCT03471182

SECTION I: RESEARCH PLAN

1. Statement of Purpose:

Cocaine use disorder (CUD) remains a significant public health concern that is resistant to current treatments. Challenges to treating CUD include an imbalance in neurobiological systems that 're-wire' the brain such that appetitive and habitual processes influence maladaptive decision-making and behavior. This research project aims to provide insight into this reorganized circuitry in CUD by investigating neurofunctional systems related to glutamatergic plasticity and functional brain networks during initial (2-5 days) abstinence. To target this potentially critical period of recovery, currently-using and non-treatment-seeking individuals with CUD will complete [¹⁸F]FPEB positron emission tomography (PET) and functional magnetic resonance imaging (fMRI) within days of admission to an inpatient research facility. Healthy comparison (HC) subjects from the community or that have participated in [¹⁸F]FPEB PET as part of other Yale approved protocols (HIC#1101007933, HIC#1111009365, HIC#2000027842/2000020186) will be recruited to participate in the fMRI portion of this study.

Aim 1: To determine the availability of mGluR5 using [¹⁸F]FPEB PET during initial abstinence in individuals with CUD. We hypothesize individuals with CUD, relative to HC, will exhibit concurrently and regionally specific increases (e.g., in the striatum) and decreases (e.g., in the prefrontal cortex) in mGluR5 availability.

Aim 2: To determine patterns of resting-state, response-inhibition, an automaticity related connectivity within and between large-scale functional networks using fMRI during initial abstinence in individuals with CUD. We hypothesize network-based analyses of fMRI will reveal lower frontoparietal and greater limbic network modulation in CUD as compared to HC.

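### The stated power (0.96 PET, 0.93 fMRI) is for one t test per modality at critical values that are not .05 cut-offs, while Aims 1 and 2 are analysed as families of tests with no primary region, primary network or multiplicity control

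*Combined protocol and SAP*

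**What the plan says.** **Hypotheses.** Section I, item 1 predicts for Aim 1 "concurrently and regionally specific increases (e.g., in the striatum) and decreases (e.g., in the prefrontal cortex) in mGluR5 availability". The regions are given only as examples. Aim 2 predicts lower frontoparietal and greater limbic network modulation, across resting-state, response-inhibition and automaticity conditions.

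**Analysis.** Section I, item 13, Standard neuroimaging analysis, specifies "regions-of-interest (ROIs) and whole-brain analyses of variance (ANOVAs) in SPM12". The regions "include basal ganglia structures, subdivisions of the cingulate and other prefrontal and parietal regions". These analyses are described as the primary investigation of mGluR5 in CUD against HC. Under Network-based analysis, independent component analysis is applied to both PET and fMRI. The number of regions, networks or components is not given.

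**Power.** Section I, item 13, Power considerations: "The proposed project will include 20 CUD and 20 HC participants". The sample is called "sufficiently powered ($d's > .95$) for analysis at a threshold of $\alpha = .05". For PET (noncentrality 3.60) the figures are "critical $t_{38} = 1.81$, power ($1 - \beta$) = 0.96"; for fMRI they are "fMRI: $\delta = 3.06$, critical $t_{38} = 1.54$, power ($1 - \beta$) = 0.93".

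The documents name no primary region or network, no voxel or cluster threshold, and no family-wise or false-discovery method. No test is declared one-sided.

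**The concern.** The power claim and the analysis describe different things. The first is a single comparison per modality. The second is a set of regional comparisons plus whole-brain maps for PET, and at least two networks for fMRI. Two consequences follow.

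- If the analysts correct for multiplicity, as is usual for whole-brain maps, the tests actually run have less power than the protocol states.
- If they do not correct, claims about individual regions or networks have no controlled error rate, and nothing in the plan separates a prespecified regional finding from one picked out of many.

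The printed critical values raise a separate issue. They do not correspond to the alpha they are labelled with, so the stated power would need correcting even if there were only one test per modality.

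**Working it through.** **Inputs from the power paragraph.** n = 20 per group, df = 38; PET noncentrality δ = 3.60, critical t = 1.81, power 0.96; fMRI δ = 3.06, critical t = 1.54, power 0.93; alpha .05, sidedness not stated. Since δ = d × √(n/2) = d × √10, the implied effects are d = 3.60/√10 = 1.14 (PET) and 3.06/√10 = 0.97 (fMRI).

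**Step 1: reproduce the stated power.** Power = P(T > critical t), with T noncentral t on 38 df.

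- PET: P(T > 1.81 | δ = 3.60) = 0.961, stated 0.96.
- fMRI: P(T > 1.54 | δ = 3.06) = 0.934, stated 0.93.

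Both reproduce at the printed critical values.

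**Step 2: what alpha do those critical values carry?**

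- 1.81 on 38 df: one-sided .039, two-sided .078.
- 1.54 on 38 df: one-sided .066, two-sided .132.

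Neither is a .05 cut-off. Those would be 1.686 one-sided and 2.024 two-sided. At one-sided .05, power is 0.971 (PET) and 0.913 (fMRI), close to the printed pair but not equal to it. The printed values match a one-sided calculation that sets alpha equal to beta (critical t 1.812 and 1.540). The protocol does not say how they were obtained.

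**Step 3: two-sided .05, then Bonferroni.** The number of tests m is an assumption, because the documents give none. Each test is two-sided at .05/m, and power is per comparison.

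| m | critical t | PET power | fMRI power |
|---|---|---|---|
| 1 | 2.024 | 0.94 | 0.85 |
| 2 | 2.334 | 0.89 | 0.76 |
| 5 | 2.712 | 0.81 | 0.64 |
| 10 | 2.980 | 0.73 | 0.54 |

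**Step 4: separate the two causes, at m = 2.**

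- fMRI: 0.93 to 0.85 comes from the cut-off and sidedness; 0.85 to 0.76 comes from multiplicity.
- PET: 0.96 to 0.94 comes from the cut-off and sidedness; 0.94 to 0.89 comes from multiplicity.

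**Step 5: false regional differences if each region were tested at uncorrected two-sided .05.** For independent regions the chance of at least one is 1 − 0.95^m: 0.40 for m = 10 and 0.64 for m = 20. For correlated regions it was simulated (20 v 20, no true differences, equal correlation between all regions, 20,000 runs).

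| Regions (assumed) | correlation 0 | 0.5 | 0.8 |
|---|---|---|---|
| 10 | 40% | 29% | 18% |
| 20 | 64% | 42–43% | 23% |

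**Step 6: a different event, at least one false increase and at least one false decrease in the same study.** With 10 regions this is about 5% at correlation 0, about 0.1% at 0.5, and none was seen at 0.8. With 20 regions it is 15%, 0.3% and none.

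**The case against.** **A reader might infer that a null study would probably confirm Aim 1.** The documents do not support this. Aim 1 predicts increases and decreases concurrently, so one nominal hit in one direction is not the predicted pattern. Step 6 gives the relevant chance: about 5% or less with 10 regions, and under 1% for either count once regions correlate at 0.5 or more. Only the case of 20 independent regions is well above 5%. The 18–40% and 23–64% figures concern any false regional difference and nothing more.

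**A reader might also infer that the plan prescribes uncorrected .05 for every region.** It does not. The .05 appears only in the power paragraph, and the analysis paragraphs state no threshold. It could be meant as a corrected level. In that case, though, the single-test power is not the power of the corrected analysis.

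**The number of tests is unknown, and Bonferroni is pessimistic for correlated regions.** Both points stand, and the rows for five and ten tests are illustrations. But the region list is plural and Aim 2 names two networks, so more than one test is certain. At two tests the fMRI figure is already 0.76.

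**The study is small and mechanistic.** Aims 3 and 4 are labelled exploratory and Aim 5 a pilot; Aims 1 and 2 are not, and they carry the hypotheses and the power claim. Aim 2 does state a direction for each of its two networks, so it is less open than Aim 1.

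**Conclusion.** The power figure is wrong as written. The stated 0.96 and 0.93 belong to a single one-directional test at critical values that do not match the stated alpha, not to the planned family of analyses. With the plan's own noncentrality parameters, a two-sided .05 test gives 0.94 (PET) and 0.85 (fMRI). With the smallest plausible primary family, two tests per modality, it gives 0.89 and 0.76 per comparison. PET power remains good at that size; the fMRI claim suffers more, and about half of its loss comes from the cut-off and sidedness rather than from multiplicity.

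The missing primary family and multiplicity rule are an omission, not a stated rule of uncorrected testing. The cost of that omission, if regions were reported at uncorrected .05, is a chance of at least one false regional difference of about 18–40% with 10 regions and 23–64% with 20. This range rests on assumed counts and on assumed equal correlations from 0.8 to 0. The effect sizes are taken from the protocol as given, since the cited studies cannot be checked here.

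**What to change.** In Section I, item 13:

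1. Name a short primary family from the aims' own wording: striatum and prefrontal cortex for Aim 1; frontoparietal and limbic networks for Aim 2.
2. Control family-wise error within each aim by Holm or by a max-t permutation test, which makes use of the correlation between regions. Use cluster-level family-wise correction for whole-brain maps. Label all other regions and networks secondary.
3. State whether Aim 1 is judged on each region separately or only on both predicted changes together. The correction and the power figures here assume the former.
4. Restate power with a correct two-sided critical value at the corrected threshold. For two tests per modality this is t = 2.334 under Bonferroni, with power of about 0.89 (PET) and 0.76 (fMRI). Holm is no less powerful than this.

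The cost is wording and a routine software option, with no new participants or procedures. The downside is that the stated power becomes less favourable, mainly for fMRI.

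### The power paragraph claims alpha = .05 but uses two different critical t values on 38 df, neither of them a .05 value, so the stated powers do not hold at that alpha

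*Combined protocol and SAP*

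**What the plan says.** Section I, item 13, Power considerations, gives 20 CUD and 20 HC participants and describes the sample as "sufficiently powered ($d's > .95$) for analysis at a threshold of $\alpha = .05". Two sets of figures follow under that one alpha. For PET, with a non-centrality parameter of 3.60, the text gives "critical $t_{38} = 1.81$, power ($1 - \beta$) = 0.96". For the functional-network comparison it gives "fMRI: $\delta = 3.06$, critical $t_{38} = 1.54$, power ($1 - \beta$) = 0.93". Sidedness is not stated and no calculation method is named. The HABIT task is then expected to have power similar to the Go/NoGo figure.

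Three other places bear on how these figures should be read:

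- Item 13, Standard neuroimaging analysis, plans "regions-of-interest (ROIs) and whole-brain analyses of variance (ANOVAs) in SPM12".
- Aim 1 (Section I, item 1) hypothesises "regionally specific increases (e.g., in the striatum) and decreases (e.g., in the prefrontal cortex) in mGluR5 availability".
- Section I, item 6 defines the 20 HC as people already scanned under another protocol, "or that are recruited from the community (Aim 5"). Section I, item 4a says of that second source: "Additional community-recruited HC individuals may be enrolled (i.e., those that have not completed" the PET scan.

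**The concern.** A critical t depends only on alpha, sidedness and degrees of freedom. All three are common to the two comparisons as the paragraph presents them, so two different values cannot both be right. If the thresholds are not .05 thresholds, the powers derived from them are not powers at .05.

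This paragraph is the only support offered for 20 per group, in a study that involves radiotracer injection, possible arterial catheterisation and an inpatient stay. A reader who tries to confirm the figures at the stated alpha cannot do so. The fMRI figure is also carried over to the HABIT task, so an error there spreads to a second task.

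**Working it through.** **Inputs, all from item 13, Power considerations.** Alpha = .05; n = 20 per group, so df = 20 + 20 − 2 = 38; delta = 3.60 (PET) and 3.06 (fMRI); printed critical t = 1.81 and 1.54; stated power = 0.96 and 0.93. Section III, item 1 gives the 20 per group as completers, so no further dropout deduction is needed.

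**Effect sizes.** With equal groups of 20, delta = d × √(20/2), so d = delta/√10. This gives 3.60/3.162 = 1.14 for PET and 3.06/3.162 = 0.97 for fMRI. Both agree with the claim that d exceeds .95, so the deltas are internally consistent.

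**Step 1: reproduce the stated powers.** Power = P(T > c), where T is noncentral t with 38 df and non-centrality delta, and c is the printed critical value.

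- PET: P(T > 1.81 | delta = 3.60) = 0.961, stated 0.96.
- fMRI: P(T > 1.54 | delta = 3.06) = 0.934, stated 0.93.

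The stated powers come from the printed thresholds, so 1.81 and 1.54 are not misprints or text-extraction faults.

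**Step 2: what alpha do those thresholds represent?** From the central t on 38 df:

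- P(t > 1.81) = 0.039 one-sided, or 0.078 two-sided.
- P(t > 1.54) = 0.066 one-sided, or 0.132 two-sided.

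The .05 critical values on 38 df are 2.024 (two-sided) and 1.686 (one-sided). Neither printed value matches either one.

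**Step 3: power at a true alpha of .05.**

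| Comparison | Stated | Two-sided (c = 2.024) | One-sided (c = 1.686) |
|---|---|---|---|
| PET, delta 3.60, d = 1.14 | 0.96 | 0.939 | 0.971 |
| fMRI, delta 3.06, d = 0.97 | 0.93 | 0.847 | 0.913 |
| Claimed floor, d = .95 | not given | 0.833 | 0.904 |

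The fMRI fall from 0.934 to 0.847 splits into 0.934 − 0.913 = 0.021 from the wrong critical value and 0.913 − 0.847 = 0.066 from reading the test as two-sided.

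**Step 4: detectable effect.** With 20 per group and 80% power, d = 0.91 two-sided or 0.80 one-sided.

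**Step 5: a possible source (inference only).** Choosing the critical value that makes one-sided alpha equal beta gives c = 1.8115 (alpha 0.039, power 0.961) for delta 3.60, and c = 1.5400 (alpha 0.066, power 0.934) for delta 3.06. All the printed figures match. This suggests that alpha was balanced against beta instead of being fixed at .05. The document names no method, and the error stands without this explanation.

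**Step 6: fewer HC with PET (assumed counts).** The documents do not say how many of the 20 HC will have PET data. Keep d = 1.14 and 20 CUD, with delta = d × √(20m/(20 + m)) for m scanned HC:

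- m = 15: delta = 3.33, df = 33, power 0.90 two-sided or 0.95 one-sided.
- m = 10: delta = 2.94, df = 28, power 0.81 two-sided or 0.89 one-sided.

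**The case against.** The strongest reply is about sidedness. Most of the fMRI drop, 6.6 of 8.7 points, comes from treating the test as two-sided, and the document does not say that it is. The hypotheses are directional: lower frontoparietal and greater limbic modulation in Aim 2, and a direction by region in Aim 1. The fMRI figure is tied to network analyses, whose paragraph names no group test. Under a one-sided .05 test PET is understated by about 1 point and fMRI overstated by about 2, which is small.

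Part of this stands. The document does not settle sidedness, so both readings must be reported, and 0.85 is conditional on the two-sided one. Two-sided is still the better-supported reading. The standard analyses are ANOVAs, and an unadjusted two-group F test on (1, 38) df at .05 has critical value 4.10 = 2.024². Whole-brain and multi-region testing with effects expected in both directions also has no single tail. In any case no choice of sidedness produces 1.81 and 1.54 together at .05.

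It can also be said that multiplicity and the HC PET count are separate design questions, and that item 4a describes the community HC as additional recruits for Aim 5. That is fair as to item 4a. Item 6, however, lists them within the 20, so the power paragraph should say what it assumes. The effect of fewer scanned HC is illustrative only and does not carry the conclusion.

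**Conclusion.** The concern holds. The paragraph's alpha and critical values contradict each other, and neither critical value is a .05 value under either sidedness. At alpha = .05 the stated fMRI power of 0.93 is too high on both readings, by about 8 points two-sided and 2 points one-sided. The stated PET power of 0.96 is about 2 points too high two-sided and 1 point too low one-sided.

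The adequacy of 20 per group is not overturned. For a single unadjusted test, power exceeds 0.80 on either reading, even at d = .95. The margin is modest two-sided (0.83 at d = .95), and nothing in it allows for the several ROIs and whole-brain tests planned.

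These results take the printed deltas as given. They assume an uncovaried two-group comparison with 20 analysable scans per group; the studies behind the effect sizes were not checked. This should be fixed, but it is a correction to the justification and not to the design.

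**What to change.** Rewrite the Power considerations paragraph in item 13:

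- State that the test is two-sided and use critical t = 2.024 on 38 df for both comparisons.
- Restate power as 0.94 for PET (d = 1.14) and 0.85 for fMRI (d = 0.97), and add that 20 per group detects d = 0.91 with 80% power.
- If a one-sided test is intended, say so and justify it. Use 1.686 for both comparisons, with power 0.97 and 0.91 and a detectable d of 0.80.
- Say that the figures apply to one unadjusted comparison with 20 scanned participants per group.
- Give the number of HC expected to contribute PET data.
- Tie the HABIT statement to the corrected fMRI figure.

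The cost is one reworded paragraph and slightly less favourable stated power on the two-sided reading. No extra participants are needed, and neither the design nor the analysis changes.
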